9.2 Subject Accountability

The number and percent of subjects enrolled who received, completed and discontinued from IP (including reasons for discontinuing), completed and discontinued the study (including reasons for discontinuing) will be summarized.

The number of subjects included in and excluded from each analysis set will be summarized.

Key study dates for the first subject enrolled, last subject enrolled, and last subject's end of study will be presented.

9.3 Important Protocol Deviations

Important Protocol Deviations (IPDs) categories are defined by the study team before the first subject's initial visit and updated during the IPD reviews throughout the study prior to database lock. These definitions of IPD categories, subcategory codes, and descriptions will be used during the course of the study. Eligibility deviations are defined in the protocol.

9.4 Demographic and Baseline Characteristics

Demographics data including sex, age, race, and ethnicity, baseline characteristics, medical history, and baseline concomitant medications will be summarized.

9.5 Efficacy Analyses

HR reduction from baseline to day 57 will be estimated from a repeated measures linear model. Summary statistics will be provided for exploratory endpoints.

9.5.1 Analyses of Primary Efficacy Endpoint(s)

The repeated measures linear model will be used to evaluate ivabradine efficacy on HR reduction from baseline to day 57 for subjects in FAS regardless of treatment adherence. The model will include terms of scheduled visits and baseline HR measurement as covariates and test whether the mean reduction with ivabradine exceeds 5 bpm, a reduction assumed with placebo. Missing values will not be imputed when the repeated measures linear model is used. Based on the model, the least-square means along with 95% confidence interval will be provided. Descriptive statistics of HR reduction by scheduled visit will also be summarized.

In addition, the primary endpoint will be analyzed within each of the subgroups (indicated in [Section 4.2](#)) using the same methodology as the primary endpoint based on the FAS of the treatment period.

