10.4.2.2 Efficacy Analyses

10.4.2.2.1 Primary Endpoint

- HR reduction from baseline to day 57 for the overall African-American/Black subjects.

[figure not shown]
The repeated measures linear model will be used to evaluate ivabradine efficacy on HR reduction from baseline to day 57 for the overall African-American/Black subjects. The model will include terms of scheduled visits and baseline HR measurement as

covariates and will test whether the mean reduction with ivabradine exceeds 5 bpm, which is the reduction assumed with placebo. Missing values will not be imputed when the repeated measures linear model is used. Based on the model, the least-square means along with 95% confidence interval will be provided. In addition, descriptive statistics of HR reduction by scheduled visit will be summarized.

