2.2 Hypotheses and/or Estimations

The primary hypothesis is that ivabradine effectively reduces HR between baseline and day 57 in African-American/Black subjects. Because mean reductions of approximately 5 beat per minute (bpm) have been observed in the overall placebo-treated subjects in the SHIFT study as well as in the placebo-treated subjects of the subgroup analysis of non-African-American/Black subjects enrolled in the SHIFT study, we will test whether the mean reduction with ivabradine exceeds 5 bpm, and estimate the degree to which the mean reduction with ivabradine exceeds 5 bpm.

3. Study Overview

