3.2 Sample Size

A minimum of 30 subjects with up to approximately 100 subjects with HFREF will be enrolled in the study.

The primary endpoint is HR reduction from baseline at day 57 greater than 5 bpm. Based on HR reduction results observed in the overall placebo-treated subjects of the SHIFT study as well as in the placebo-treated subjects of the subgroup analysis of non-African-American/Black subjects enrolled in the SHIFT study, the mean change HR in the ivabradine group was 13 bpm with a standard deviation of 10.4 bpm at end of 28 days and maintained until end of study. In addition, the mean change in the placebo group was 5 bpm observed at end of 28 days, so the hypothesis is to evaluate the HR reduction from baseline at day 57 greater than 5 bpm. Based on a 2-sided, 1-sample t-test with significance level of 0.05, the planned sample size of 30 to 100 subjects will provide approximately 97% to >99% power. The sample size considerations incorporate an assumption of a study drop out of 10%.

4. Covariates and Subgroups

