9.5.2 Sensitivity Analysis of Primary Endpoint(s)

[figure not shown]
To evaluate the robustness of the analysis results, sensitivity analyses will be performed as follows:

[figure not shown]
- A sensitivity analysis will be performed using multiple imputation. **The primary analysis model will be repeated using FAS with missing values imputed. Missing values from patients who discontinued IP will be imputed using non-missing data from subjects who discontinued IP while missing values from patients who completed IP will be imputed using non-missing data from subjects who completed IP, provided that there is a sufficient number of subjects with non-missing endpoint data in both groups.**
- Analysis of covariance (ANCOVA) will be performed for day 57 data using covariates (described in [Section 4.1](#)) in the same model

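### With one arm and a fixed 5 bpm benchmark, the confidence interval of the baseline-adjusted Day 57 mean is too narrow for the population mean reduction

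*SAP*

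**What the plan says.** SAP 2.2 sets two aims for African-American/Black subjects on ivabradine. The first is a test: "we will test whether the mean reduction with ivabradine exceeds 5 bpm". The second is to "estimate the degree to which the mean reduction with ivabradine exceeds 5 bpm".

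SAP 9.5.1 assigns both to a repeated measures linear model: "The model will include terms of scheduled visits and baseline HR measurement as covariates and test whether the mean reduction" is more than 5 bpm. It adds: "Based on the model, the least-square means along with 95% confidence interval will be provided". Protocol 10.4.2.2.1 describes the same model, with visit and baseline heart rate as "covariates and will test whether the mean reduction with ivabradine exceeds 5 bpm". Neither document gives the baseline value at which the least-squares mean is evaluated, says whether the target is conditional on the observed baselines, or specifies a standard error that treats baseline as random.

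The sizing in SAP 3.2 uses a different procedure: "Based on a 2-sided, 1-sample t-test with significance level of 0.05". Its inputs are that "the mean change HR in the ivabradine group was 13 bpm with a standard deviation of 10.4 bpm at end of 28 days" and that the placebo change was 5 bpm.

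Among the sensitivity analyses in SAP 9.5.2, "Analysis of covariance (ANCOVA) will be performed for day 57 data using covariates", and SAP 4.1 lists those covariates as age, sex and baseline heart rate.

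**The concern.** In a two-arm trial, error in the overall sample mean baseline drops out of the treatment difference. Here nothing is subtracted, because the adjusted mean itself is compared with 5 bpm. If it is evaluated at the sample mean baseline, the model standard error reflects only residual scatter about the regression on baseline. A new sample from the same population would have a different mean baseline and, if change depends on baseline, a different mean change. That part of the uncertainty is missing.

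The estimation aim is the one mainly at stake. The 95% interval for how far the reduction exceeds 5 bpm would cover the population value less often than stated. The test is affected to a practical degree only if the true reduction lies near 5 bpm.

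No other planned analysis supplies a corrected test or interval. Multiple imputation and the subgroup analyses reuse the same model, the ANCOVA has the same omission, and the by-visit summaries are descriptive and use observed cases only.

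**Working it through.** **The plan's own figure.** Difference from the null 13 − 5 = 8 bpm, SD 10.4, two-sided 0.05, one-sample t-test (noncentral t). With 10% dropout, 30 to 100 enrolled gives 27 to 90 evaluable.

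- Power at n = 27 is 97.0% and at n = 30 is 98.3%.
- Power at n = 90 and n = 100 is above 99.9%.

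The stated 97% to >99% is reproduced, and the 97% corresponds to 27 evaluable subjects.

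**The omitted term.** Let Y be change in heart rate with SD σ, X baseline heart rate, b the slope of Y on X, and r their correlation. With complete data, the adjusted mean at the sample mean of X is simply the sample mean of Y, so adjustment adds no precision for the population mean.

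- True variance: σ²/n = σ²(1 − r²)/n + b²·Var(X)/n.
- Model variance: σ²(1 − r²)/n only.
- Ratio of model SE to true SE: √(1 − r²), whatever n is.

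For example, at n = 27 the true SE is 10.4/√27 = 2.00 bpm. At r = 0.3 the model gives 2.00 × √0.91 = 1.91; at r = 0.5 it gives 2.00 × √0.75 = 1.73.

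**Effect on error rates.** Single-visit ANCOVA, adjusted mean at the sample mean baseline, true reduction 5 bpm, SD 10.4, 100,000 simulated trials per cell. The values of r are assumed.

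| r | SE understated | Type I error, n = 27 | Type I error, n = 90 | Coverage, n = 27 |
|---|---|---|---|---|
| 0 | 0% | 5.0% | 5.1% | 95.0% |
| 0.15 | 1.1% | 5.2% | 5.3% | 94.8% |
| 0.3 | 4.6% | 6.0% | 6.2% | 94.0% |
| 0.5 | 13.4% | 8.6% | 9.0% | 91.4% |

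Repeat runs differ by at most about 0.4 percentage points. The one-sample t-test stays at about 5% throughout. In the benefit direction alone, the nominal 2.5% becomes about 3.0% at r = 0.3 and 4.3% at r = 0.5 (n = 27).

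**The two-visit model.** With Days 15 and 57, a common slope, unstructured covariance and an assumed between-visit correlation of 0.5, type I error is 6.3% (n = 27) and 5.9% (n = 90) at r = 0.3, and 8.7% and 8.6% at r = 0.5.

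**Interval width.** Half-widths from t × SE with σ = 10.4 plugged in:

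| n | Correct | Model, r = 0.3 | Model, r = 0.5 |
|---|---|---|---|
| 27 | 4.11 bpm | 3.93 bpm | 3.57 bpm |
| 90 | 2.18 bpm | 2.08 bpm | 1.89 bpm |

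Average simulated widths at n = 27 are about 0.04 bpm lower in each column, with the same gaps.

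**What r is plausible.** The SAP defines change as post-baseline minus baseline, so baseline measurement error enters both sides, and entry requires at least 70 bpm at screening and Day 1. Regression to the mean was simulated with assumed within-subject SD 4–6, between-subject SD 8–9 and mean true heart rate 75–80 bpm. Holding the SD of change at 10.4, it alone gives r of about 0.15 to 0.31, hence type I error of about 5.2% to 6.2%. A larger r requires a drug response that rises with baseline, which is a further assumption.

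**Effect on the verdict.** At a true 13 bpm reduction and n = 27, the model is significant where the t-test is not in 0.6% (r = 0.3) to 1.4% (r = 0.5) of trials; at n = 90, 0.0%.

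**The case against.** The strongest reply is that covariate-adjusted inference is normally conditional on the covariates, and for the mean at the observed baselines the interval is valid. On that reading the gap is one of stating the target. But the SAP does not state the conditional target, and its hypothesis concerns African-American/Black subjects generally. Naming the full analysis set in SAP 9.5.1 does not settle the matter.

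The size also depends on two things the documents do not give: evaluation at the sample mean baseline, and r. In the range that regression to the mean supports, the effect is small. At r = 0.3 the half-width gap is 0.18 bpm at n = 27 and 0.10 bpm at n = 90, against a benchmark that is itself only approximately 5 bpm. The r = 0.5 figures need an extra assumption, and the verdict at 13 bpm hardly moves. All of this stands, and it limits the seriousness of the point.

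The by-visit summaries will include n, mean and SD or SE, so a reader could rebuild the unadjusted interval. That helps, but it is not a pre-specified inference. It also uses completers only: if about 10% of Day 57 values are missing, more often at high baseline (an assumed mechanism), the completer mean is biased by 0.23 bpm at r = 0.3 and 0.39 bpm at r = 0.5.

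Sizing on an unadjusted SD and analysing with a covariate is common and not an error in itself. Here, though, the apparent gain from adjustment is not real precision for the population mean.

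**Conclusion.** The concern holds. For the population mean reduction, with the least-squares mean taken at the sample mean baseline, the planned standard error is too small by the factor √(1 − r²) at any sample size in the planned range. If r is about 0.15 to 0.31 the cost is modest: roughly 0.2 to 1.2 percentage points of type I error, with a matching loss of coverage. If r reaches 0.5, coverage falls to about 91%. The algebra is certain; the size is conditional on r. The damage falls mainly on the estimation aim and on results near 5 bpm. At the planning assumptions the yes/no conclusion is safe. The point should be fixed, but it does not invalidate the trial.

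**What to change.** State in SAP 9.5.1 and protocol 10.4.2.2.1 that the target is the population mean reduction at Day 57. Then choose one of two routes before database lock.

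1. Model heart rate itself at the SAP-defined baseline, Day 15 and Day 57 as responses, with unstructured covariance and no baseline covariate. Test Day 57 minus baseline against −5 bpm. With complete data this gives the one-sample t estimate and standard error that the sizing assumes, and it still uses the baseline of subjects who miss Day 57.
2. Keep the covariate model, evaluate the least-squares mean at the mean baseline of all full-analysis-set subjects, and add b²·s²(baseline)/n to its squared standard error, or bootstrap subjects. With the missing-data assumptions above, the added term brings type I error at r = 0.3 from 5.9% to 4.6% (30 enrolled) and from 6.0% to 4.9% (100 enrolled), with no bias in the estimate. It is therefore slightly conservative at the smaller size.

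Apply the matching change to the multiple imputation, ANCOVA and subgroup analyses.

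The cost is one paragraph in each document and no new data. The stated 97% power stands, since it was computed from the unadjusted SD.

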4.2 Subgroups

- Age: < 65 years, ≥ 65 years
- Sex
- Baseline HR (< 77 bpm, ≥ 77 bpm)

A subgroup variable will be eliminated if one of the two subgroup levels is <10% of overall group.

5. Definitions

Treatment Emergent Disease-Related Event

Events categorized as Disease-related Events (DREs) starting on or after first dose of investigational product as determined by the flag indicating if the event started prior to the first dose on the Events eCRF and up to the EOS/Safety Follow-up visit or 30 days after the last administration of investigational product (IP), whichever is earlier.

Treatment Emergent Adverse Event

Events categorized as Adverse Events (AEs) starting on or after first dose of investigational product as determined by the flag indicating if the event started prior to the first dose on the Events eCRF and up to the EOS/Safety Follow-up visit or 30 days after the last administration of IP, whichever is earlier.

Treatment Emergent Serious Adverse Event

Treatment emergent adverse events (as defined above) that are indicated as serious on the Events eCRF.

End of Investigational Product (EOIP) Date

For each subject, the end of investigational product date is defined as the date recorded in the EOIP administration form,

Last Dose Date

For each subject, the last dose date is defined as the stop date on the last record of administration of IP page.

End of Study (EOS) Date

For each subject, the End of Study Date is the date recorded on the End of Study eCRF.

Baseline

For all variables, the baseline value is defined as the last non-missing value collected prior to or on Study Day 1.

Change from Baseline

The arithmetic difference between a post-baseline value and the baseline value:
Change (absolute) from Baseline = (Post-baseline Value – Baseline Value)

Percent change from Baseline

Percent Change from Baseline = $[(\text{Post-baseline Value} - \text{Baseline Value}) / \text{Baseline Value}] \times 100$

Enrollment Date

Enrollment Date is defined as the date collected on the Subject Enrollment eCRF.

Investigational Product (IP)

The term investigational product is used in reference to Ivabradine.

Study Day 1

Day 1 is defined as the day that IP is first administered to the subject. If a subject enrolled but never received IP, Study Day 1 is defined as the enrollment day.

Study Day

For each subject, and for a given date of interest, Study Day is defined as the number of days since Study Day 1:

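### Testing the <77 and ≥77 bpm baseline-HR subgroups against the overall 5 bpm placebo figure mixes regression to the mean into the subgroup results

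*SAP*

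**What the plan says.** SAP 4.2 lists, beside age and sex, the subgroup variable "Baseline HR (< 77 bpm, ≥ 77 bpm". SAP Section 5 (Definitions) states that "the baseline value is defined as the last non-missing value collected prior to or on Study Day 1", and forms the change by subtracting that same value from the post-baseline value. SAP 9.5.1 fits a repeated measures model with visit and baseline HR and tests the reduction against 5 bpm. It then adds that "the primary endpoint will be analyzed within each of the subgroups" with the primary methodology, so each subgroup inherits the 5 bpm test.

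The benchmark comes from SAP 2.2, where reductions of about 5 bpm "have been observed in the overall placebo-treated subjects in the SHIFT study", and from SAP 3.2: "the mean change in the placebo group was 5 bpm observed at end of 28 days". No value by baseline-HR level is given. The trial has no control arm. Neither document calls the subgroup results descriptive only or mentions regression to the mean.

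**The concern.** One reading does two jobs. A subject whose reading is high by chance on Day 1 is placed in ≥77, and the same chance error enlarges the later fall. A subject whose reading is low by chance is placed in <77, and the error shrinks the fall or turns it into a rise. The expected change without drug therefore differs between the two groups and is not 5 bpm in either, even if it is 5 bpm overall.

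Baseline HR as a covariate does not remove this, because the model is refitted within each subgroup. With least-square means taken at the mean baseline of the subjects in the fit (the usual default; the SAP does not say), the estimate reproduces that subgroup's own biased mean.

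At stake is the reading of a pre-specified result. The tables may suggest that ivabradine lowers heart rate more when baseline heart rate is higher. Without a control arm, the trial's data cannot separate that from the artefact.

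**Working it through.** **1. The plan's own figure.** SAP 3.2: "Based on a 2-sided, 1-sample t-test with significance level of 0.05"; "the mean change HR in the ivabradine group was 13 bpm with a standard deviation of 10.4 bpm"; benchmark 5. The planned excess is 13 − 5 = 8 bpm. With 10% dropout, 30 to 100 subjects become 27 to 90 evaluable. The noncentrality is 8/(10.4/√27) = 4.00, which gives 97.0% power; at 90 it is 8/(10.4/√90) = 7.30, which gives more than 99%. The stated power reproduces. The nominal rate of a false finding in the favourable direction is 0.05/2 = 2.5%.

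**2. Mechanism.** Let the observed HR be usual HR plus independent reading error, with between-subject SD s_b and within-subject SD s_w. Before selection, the expected fall from reading error alone, for a baseline reading b, is (b − mean) × s_w²/(s_b² + s_w²). For s_b = 8:
- s_w = 4: 16/(64 + 16) = 0.20 bpm per bpm of baseline
- s_w = 6: 36/(64 + 36) = 0.36 bpm per bpm of baseline

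The share is above zero whenever s_w is above zero, so the direction does not depend on the assumed values; the size does.

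**3. Assumptions for the size.** The documents give neither a baseline HR distribution nor a within-subject SD. Assumed: usual HR mean 72-80, s_b 7-9, s_w 4-6. Entry requires HR ≥70 at screening (Protocol 6.1, criterion 106) and on Day 1 (SAP 3.1). The drug effect is the same for everyone, and the overall mean reduction is set to exactly 5. Screening, Day 1 and Day 57 readings were simulated.

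**4. Two central cases** (mean 75, s_b 8):

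| s_w | Reduction in <77 | Reduction in ≥77 | Gap |
|---|---|---|---|
| 4 | 3.25 | 6.00 | 2.75 |
| 6 | 1.76 | 6.62 | 4.86 |

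Since the overall mean is 5, the share in <77 is (6.00 − 5)/2.75 = 36% for s_w = 4 and (6.62 − 5)/4.86 = 33% for s_w = 6.

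Over the whole assumed range: 0.7-3.5 bpm in <77, 5.6-7.1 bpm in ≥77, gap about 2.5-5.7 bpm.

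**5. Effect on the test in ≥77.** Take s_w = 4 and 90 evaluable. About 90 × 0.64 = 57 subjects fall in ≥77, and the noncentrality is (6.00 − 5)/(10.4/√57) = 0.73, which gives a false finding in about 11% instead of 2.5%. Over the assumed range:

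| SD of change | 27 evaluable | 90 evaluable |
|---|---|---|
| 10.4 (SAP 3.2) | about 5-11% | about 7-29% |
| Implied by the assumed reading error | about 7-16% | about 15-48% |

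The first row combines an SD of 10.4 with inputs that by themselves imply an SD of change of only about 5.4-8.2. Both rows are shown because the documents do not settle which is nearer the truth.

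**6. Splitting on the screening ECG.** In the same two cases the reductions become 5.63 (<77) and 4.64 (≥77) for s_w = 4, and 5.97 and 4.52 for s_w = 6. The differences are 0.99 and 1.45 bpm, in the opposite direction. Over the assumed range they are about 0.7-1.7 bpm. They remain because Day 1 also requires HR ≥70.

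**The case against.** The strongest reply is that little hangs on this. The hypothesis concerns subjects overall (Protocol 4.2, SAP 2.2). Protocol 10.2.3 says only that subgroups might include age and sex. No document gives the subgroups an alpha, a success criterion or a between-group comparison. That stands, and it limits the weight of the point. It does not make 5 bpm the right reference for a group selected on the baseline reading.

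A reader might infer that ≥77 will succeed and <77 will fail. The documents do not support that. At the planned reduction of 13 bpm, 8 above the benchmark, the expected <77 values become 0.7 + 8 = 8.7 to 3.5 + 8 = 11.5 bpm, still above 5, so both groups may exceed it. A non-significant <77 result could also be plain lack of size: about 9 subjects at SD 10.4 have only 53% power for an 8 bpm excess with no bias at all.

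It is also fair that the error rates rest on assumed variances. The direction is firm; the rates are a range.

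The rule that "A subgroup variable will be eliminated if one of the two subgroup levels is <10% of overall group" is no answer, since it concerns group size and not this bias.

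**Conclusion.** The point holds as a limited one. SAP 4.2, 5 and 9.5.1 together use one reading both to classify subjects and to form the change, then test each class against an overall placebo mean. Given any within-subject reading error, this overstates the reduction in ≥77 and understates it in <77. Under the assumptions above the spurious gap is about 2.5-5.7 bpm, and the chance of a false finding in ≥77 is above 2.5%: about 5-16% with 27 evaluable and 7-48% with 90, across both choices of SD. The subgroup results may therefore suggest a larger effect at higher baseline HR.

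It would go too far to infer that the primary conclusion is compromised: this split does not enter the overall test.

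**What to change.** - **SAP 9.5.1:** report the baseline-HR subgroups as estimates with 95% confidence intervals, without the 5 bpm test, and state that differences between them include regression to the mean.
- **SAP 4.2:** define these subgroups by the screening ECG heart rate, which is already collected. Under the Section 5 definition the screening value becomes the baseline when the Day 1 value is missing, so leave such subjects out of this subgroup analysis.
- **State the residual:** a small bias in the opposite direction remains, about 0.7-1.7 bpm under the assumptions above, because Day 1 also requires HR ≥70.

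Presenting the fitted change across baseline HR from the primary model is not a substitute. It regresses the change on the same reading, and under the assumptions above its fitted values at the two subgroup means still differ by about 2.3-5.5 bpm.

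The cost is SAP wording only. There would be no pass/fail statement for the HR subgroups, and possibly a few subjects would be left out of them.

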10.2.3 Subgroups

Subgroups might include, but are not limited to:

- Age: < 65 years, ≥ 65 years
- Sex

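### SAP 9.5.1 repeats the 5 bpm test separately in up to six subgroup levels, with no exploratory label and no comparison between levels, so at small N it will often suggest effect modification that is not there

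*SAP*

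**What the plan says.** SAP 9.5.1 fits a repeated measures model in the full analysis set (FAS) with visit and baseline HR as terms. It uses the model to "test whether the mean reduction with ivabradine exceeds 5 bpm, a reduction assumed with placebo", and reports least-squares means with 95% confidence intervals. The next paragraph, still under the primary-endpoint heading, adds that "the primary endpoint will be analyzed within each of the subgroups" of SAP 4.2 by the method used for the primary endpoint. That method includes the 5 bpm test.

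SAP 4.2 lists age (below 65, 65 and over), sex, and "Baseline HR (< 77 bpm, ≥ 77 bpm". That gives 3 × 2 = 6 levels at most, because a factor is dropped if one of its levels holds under 10% of subjects.

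The only stated significance level is in SAP 3.2: "Based on a 2-sided, 1-sample t-test with significance level of 0.05". SAP 9.5.1 gives neither an alpha nor a sidedness.

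Protocol 10.4.2.2.1 describes the primary analysis with no subgroup test. Protocol 10.2.3 says only "Subgroups might include, but are not limited to" age and sex. In the text that can be read, neither document calls the subgroup results exploratory or descriptive, places them after the overall test, or plans a between-level comparison.

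**The concern.** A subgroup analysis is normally read as an answer to whether the response differs by age, sex or baseline HR. Testing each level separately against a constant does not answer that. A level passes or fails largely according to how many subjects it holds. Two levels with the same true effect can therefore fall on opposite sides of 0.05, and the pair is then easily read as a drug that works in one group and not in the other.

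There is a second, smaller risk. If the drug does no better than the benchmark, one of several levels may exceed 5 bpm by chance. The SAP contains no sentence marking such a result as non-confirmatory.

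Both matter most near the lower end of the planned 30 to 100 subjects, where a level may hold only a handful of people.

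**Working it through.** **Inputs (SAP 3.2).** "the mean change HR in the ivabradine group was 13 bpm with a standard deviation of 10.4 bpm"; benchmark 5 bpm, so the assumed excess is 13 − 5 = 8 bpm. "The sample size considerations incorporate an assumption of a study drop out of 10"%, so 30 × 0.9 = 27 and 100 × 0.9 = 90 evaluable subjects. Test: one-sample t, 2-sided 0.05.

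**The plan's own power figure.** The noncentrality is (8 / 10.4) × √27 = 4.00, and the critical t on 26 df is 2.056. Power is 97.0% at n = 27 and above 99.9% at n = 90. This reproduces "the planned sample size of 30 to 100 subjects will provide approximately 97% to >99% power" and supports reading the tests as 2-sided 0.05 after dropout.

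**If the drug does no better than the benchmark.** Every level truly has a mean reduction of 5 bpm.
- Upper reference, six independent tests, favourable tail only: 1 − 0.975⁶ = 14.1%.
- The six levels reuse the same subjects, so the true figure is lower. Simulation (20,000 trials per setting; n = 27 and 90; three independent factors; level splits from 50:50 to 80:20; the under-10% rule applied) gives about 11% for at least one level significantly above 5 bpm.
- In about 8–9% of trials this happens without a favourable overall result.
- The overall test itself rejects in about 5% of trials (about 2.5% favourably), as it should.

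**If the drug works exactly as assumed, identically in every level.** Power within a level of size n, with excess 8 bpm and SD 10.4:

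| n in level | 5 | 13 | 14 | 18 | 22 | 45 |
|---|---|---|---|---|---|---|
| Power | 26.4% | 72.1% | 75.8% | 86.8% | 93.0% | 99.9% |

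The two levels of a factor share no subjects, so the chance that exactly one is significant is p₁(1 − p₂) + p₂(1 − p₁).
- 27 subjects split 13 and 14: 0.721 × 0.242 + 0.758 × 0.279 = 0.39.
- 27 subjects split 5 and 22: 0.264 × 0.070 + 0.930 × 0.736 = 0.70.
- 90 subjects split 45 and 45: 2 × 0.999 × 0.001 = 0.002.
- 90 subjects split 18 and 72: power in the larger level is essentially 100%, so 1 − 0.868 = 0.13.

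Over three factors, simulated, the chance that at least one factor has one level significant and the other not is:

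| Larger-level shares of the three factors | 27 evaluable | 90 evaluable |
|---|---|---|
| 50, 50, 50% | 64–65% | about 1% |
| 70, 65, 50% | 76% | about 6% |
| 80, 80, 60% | 88% | 26–27% |

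**The alternative.** A direct test of the between-level difference, one per factor at 0.05, gives a false difference somewhere in about 1 − 0.95³ = 14% of trials, whatever the sample size. Simulation agrees (about 14%). With 90 subjects and even splits the separate tests mislead less often than this. With 27 subjects they mislead far more often.

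**Precision of the alternative.** The 95% half-width of a between-level difference is t × 10.4 × √(1/n₁ + 1/n₂). For 13 and 14 subjects: 2.060 × 10.4 × 0.385 = 8.2 bpm. For 45 and 45: 1.987 × 10.4 × 0.211 = 4.4 bpm.

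**The case against.** The best defence is that nothing depends on the subgroups. There is one primary hypothesis, in the overall population, and no success rule or claim uses a subgroup result. The subgroup paragraph follows the overall analysis as an addition, the specified output is means with intervals, and the protocol's subgroup wording is optional. No stated objective concerns differences between levels, and age, sex and baseline HR already enter the sensitivity ANCOVA. All of this stands, and it limits the point to interpretation. It does not remove the instruction to apply the 5 bpm test level by level. ANCOVA terms for age and sex also do not estimate whether the Day 57 change differs by level unless those terms are reported for that purpose.

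Three stronger readings are tempting and are not supported.
- A reader might count every significant level in either direction, find about 21%, and call it a fourfold family-wise inflation of alpha. The hypothesis is directional, so about half of those events are levels significantly below 5 bpm, which nobody would report as efficacy. The documents also declare no family of seven tests.
- A reader might say that the subgroup tests are specified at full alpha. The level is inferred from the sample size text; SAP 9.5.1 states none.
- A reader might say that the protocol's open subgroup list leaves the factors undefined. SAP 4.2 already fixes three factors with cut-points.

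The calculation is also open to fair criticism. It uses one-sample t-tests in place of the repeated measures model, treats the factors as independent, and assumes the splits. Correlated factors would lower the null figures. If the change depends on baseline HR, the assumption of a common effect in both baseline-HR levels fails and some apparent differences would be real.

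**Conclusion.** The point holds as a weakness of method and labelling in the subgroup analysis. It is not a loss of control of the primary type I error.

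The main cost is spurious contrast between levels: about 64–88% of trials at 27 evaluable subjects and about 1–26% at 90, when the effect is the same everywhere. The chance of a falsely favourable level when the drug only matches the benchmark is about 11%, or 8–9% without a favourable overall result. These figures rest on normal data with SD 10.4, independent factors, level splits from 50:50 to 80:20, one-sample t-tests, and 2-sided 0.05 carried over from the sample size section. The documents give no expected splits, so the ranges matter more than any single value.

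It is worth changing because a better method is available on data already being collected. If enrolment ends near 100 with balanced levels, the practical difference is small.

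**What to change.** In SAP 9.5.1:
- Replace the within-level tests against 5 bpm by the Day 57 least-squares mean and 95% CI for each level, with no p-value against 5 bpm.
- For each factor, fit one model in the whole FAS with a subgroup-by-visit term, and report the Day 57 between-level difference with its 95% CI. For the baseline HR factor, say how the two-level term and the continuous baseline HR term are handled together.
- State that the subgroup results are exploratory and that the overall FAS Day 57 test against 5 bpm is the only confirmatory test.

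The protocol's subgroup list needs no change.

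The cost is a few sentences and three model runs, with no new data. The downside is imprecision: near N = 30 the half-width of a between-level difference is about as large as the 8 bpm effect the study is built to detect. The interval shows that openly, whereas six separate verdicts would conceal it.
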